10.4.2 Secondary Endpoints

Acceptability Endpoint

To evaluate acceptability, the proportion of participants who at their 12-Week Final Clinic Visit report via acceptability questionnaire that they prefer the ring at least as much as other HIV prevention methods. A sample size of 72 females receiving the dapivirine VR will provide an absolute precision of 10.5% (i.e., half the width of the 95% confidence interval) assuming an observed acceptability of 75%.

Adherence Endpoint

Adherence will be measured by the percentage of women who keep the VR inserted at all times in the vagina over the course of 12 weeks. A sample size of 96 women will provide an absolute precision of 9.1% (i.e., half the width of the 95% confidence interval) assuming an observed adherence of 75%.

Pharmacokinetic Endpoints

The PK endpoint is a description of the end of period (28 day post ring insertion) plasma, vaginal fluid, and cervical tissue dapivirine concentrations at week 4, 8, and 12 which will be compared to the same results in a recently studied population of premenopausal adult women (MTN-013). The 28 day assessment in each ring period – just before ring removal – represents near steady-state concentrations in prior dapivirine ring studies. The intent is to determine if the plasma and vaginal fluid dapivirine concentrations are different in postmenopausal women than in premenopausal adult women after placement of dapivirine vaginal rings. The vaginal fluid will be collected by tear strip and the cervical tissue will be collected by biopsy in only a subset of women, 45 for tear strip and 15 for biopsy. This more intensively sampled subset was selected to provide a richer dataset of sampling from the female genital tract and chosen to balance feasible logistical complexity which demands a simpler, more sparse sampling approach with the low likelihood of an important difference between postmenopausal and premenopausal adult populations.

Approximately 45 women will provide vaginal fluid. The CV% ranges from 118% to 153% depending on time, location, and formulation. Also, there is no evidence of dose-proportionality for the increase from 0.001% dapivirine gel to 0.005% gel, there is no increase (due to either no difference or insufficient power to detect the difference). If one assumes a CV% of 130%, and comparison of MTN-013 (N=12) to MTN-024 (N=22), then with 5% type I error and 80% power, we can exclude a difference as large as 1.04 SD units or a 135% difference.

Approximately 15 women will provide cervical tissue. There are insufficient data published to estimate CV%, but it appears to be quite large. Nel²⁶ reports a range of tissue dapivirine concentration from 1-43, 1-190, and 1-356 for 0.001, 0.005, and 0.02% dapivirine gel, respectively. If this had the same variation as tenofovir in tissue, the CV% would be 210-240%. So, if one were to assume tenofovir tissue variability and compare MTN-024 (assuming N=11 due to 3:1 randomization) to MTN-013 (N=12 in each arm), then with 5% type I error and 80% power, we can exclude a difference as large as 1.23

SD units or a 275% difference. The sample size estimates are not different whether one assumes equal or unequal variance.

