3.2 Secondary Objectives

Acceptability

- To evaluate acceptability of study VR expressed as women's preference for the VR compared to other HIV prevention methods in HIV-uninfected postmenopausal women, when inserted once every 4 weeks during the 12 week study product use period

Adherence

- To evaluate the adherence to a 4-week regimen of dapivirine VR as compared to placebo VR over 12 weeks of use

Pharmacokinetics

- To evaluate the local and systemic dapivirine exposure

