10.4 Sample Size and Power Calculations

10.4.1 Primary Endpoints

The proposed total sample size is approximately N=96 postmenopausal females randomized to 2 arms in a 3:1 ratio giving 72 postmenopausal females in the dapivirine VR arm and 24 postmenopausal females in the placebo VR arm. The sample size is based upon the size of similar Phase 2a studies of vaginal microbicide products and includes a 3:1 ratio of drug to placebo arms to allow for the collection of additional safety endpoints in the drug arm while maintaining blinding between arms.

As a means to characterize the statistical properties of this study Table 10 presents the probability (expressed as a percent) of observing zero, at least one, and two or more safety endpoints among the 72 postmenopausal females in the dapivirine VR arm for various 'true' event rates.

Table 10: Analysis of Safety Event Frequency

Event Rate (%)	P (0 events n=72) (%)	P (≥ 1 event n=72) (%)	P (≥ 2 events n=72) (%)
0.5	69.7	30.3	5.1
1.0	48.5	51.5	16.2
3.5	7.7	92.3	72.2
5	2.5	97.5	88.1
10	0.05	99.95	99.5
15	0.0	99.99	99.99

An alternative way of describing the statistical properties of the study design is in terms of the true rate based on the observed data. Table 11 shows the exact 2-sided 95% confidence intervals for the probability of an event based on a particular observed rate. For example, if none of the 72 participants using the dapivirine VR experiences a safety event, the 95% exact 2-sided confidence interval for the true rate of event is (0.0%, 4.99%). If we see 2 events, this changes to (0.34%, 9.68%).

Table 11: Exact Two-sided 95% Confidence Intervals Based on Observing a Particular Rate of Safety Endpoints for Arms of Size 72

Observed event rate (%)	Confidence interval (%)
0.0 (0/72)	(0.0, 4.99)
1.4 (1/72)	(0.04, 7.50)
2.8 (2/72)	(0.34, 9.68)

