10.8.3 Secondary Analyses

Acceptability

To assess product preference of the study product, the number and percentage of participants who report that they prefer the ring at least as much as other HIV prevention methods (e.g., condom) will be calculated by arm.

Adherence

The average rate of VR use will be calculated in both arms along with 95% confidence intervals. These rates will be based on participant's self-report of product use at 4, 8, and 12 weeks. The difference between adherence rates with its corresponding 95%

confidence interval will be used to assess adherence of the study product compared to placebo.

Pharmacokinetics

A population mean and standard deviation of the end-of-period dapivirine concentrations for each woman will be calculated based on the samples obtained as described above. The population mean from this study will be compared to the population mean and standard deviation from similar end of period dapivirine results for each matrix – plasma, vaginal fluid, and cervical tissue – in MTN-013.

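### The adherence precision of 9.1% is for one proportion pooled over 96 women, but the planned comparison is 72 vs 24, where the half-width is about 20 points; the adherence measure also differs between sections

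*Protocol*

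**What the plan says.** The adherence objective in section 3.2 is comparative: "To evaluate the adherence to a 4-week regimen of dapivirine VR as compared to placebo VR over 12 weeks of use". Section 10.2 repeats the comparison with placebo and lists the endpoint as self-reported measures of daily product use.

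Section 10.4.2 defines a yes/no measure for each woman, with the period counted in weeks: "Adherence will be measured by the percentage of women who keep the VR inserted at all times in the vagina over the course of 12". It then gives one precision figure: "A sample size of 96 women will provide an absolute precision of 9.1% (i.e., half the width of the 95% confidence interval"). The value behind that figure is a single one, given as "assuming an observed adherence of 75"%. Section 10.4.1 sets the arm sizes, "giving 72 postmenopausal females in the dapivirine VR arm and 24 postmenopausal females in the placebo VR arm", so 96 is both arms together.

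Section 10.8.3 describes the analysis differently: "The average rate of VR use will be calculated in both arms along with 95% confidence intervals", based on self-report at weeks 4, 8 and 12. The comparison with placebo rests on a contrast and its interval: "The difference between adherence rates with its corresponding 95"%. It plans no estimate pooled over the two arms.

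**The concern.** Two things do not match between the planning text and the analysis text.

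- **The quantity that is sized.** The only precision figure for adherence belongs to a single proportion in all 96 women. The analysis reports each arm and the difference. With 3:1 allocation, the 24 placebo women dominate the uncertainty of the difference, so its precision is much poorer than that of a pooled proportion. The protocol gives no figure for either arm or for the difference.
- **The measure.** Section 10.4.2 uses a strict yes/no classification over 12 weeks; 10.8.3 uses an average rate of use. The two can rank the same woman differently. If the average rate is read as a share of time, a woman with one short removal fails the first measure and still scores high on the second.

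At stake is what a reader expects of a secondary objective. Someone who takes the only stated figure as a guide to the adherence comparison would expect less than half the uncertainty that the design delivers. Without one fixed measure, it is also unclear which result answers the objective.

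**Working it through.** **Inputs.** Pooled N = 96, adherence p = 0.75 and 95% confidence (10.4.2); arms of 72 and 24 (10.4.1). At 75% the counts are 72/96, 54/72 and 18/24. The per-arm and difference calculations assume 75% in each arm, since the protocol gives one value only.

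**1. Reproduce the stated figure.** The exact (Clopper-Pearson) 95% interval for 72/96 is 65.12% to 83.28%. Half-width = (83.28 - 65.12)/2 = 9.08 points, which matches 9.1. The simple Wald formula gives 1.96 × √(0.75 × 0.25/96) = 8.66, so the protocol evidently used the exact method. The same method reproduces the acceptability precision in the same section: 54/72 gives 63.40% to 84.46%, half-width 10.53 against a stated 10.5.

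**2. Each arm, exact method.**

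| Arm | Count | 95% interval | Half-width |
|---|---|---|---|
| Dapivirine | 54/72 | 63.4% to 84.5% | 10.5 points |
| Placebo | 18/24 | 53.3% to 90.2% | 18.5 points |

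**3. The difference, 72 vs 24.**

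- Wald: 1.96 × √[0.75 × 0.25 × (1/72 + 1/24)] = 1.96 × √(0.1875 × 0.05556) = 0.200, or 20.0 points.
- Newcombe, from the Wilson limits 0.6391 to 0.8356 (54/72) and 0.5510 to 0.8800 (18/24):
  - lower = -√[(0.75 - 0.6391)² + (0.8800 - 0.75)²] = -0.171
  - upper = √[(0.8356 - 0.75)² + (0.75 - 0.5510)²] = 0.217
  - that is -17.1 to +21.7 points, half-width 19.4.
- Wald with continuity correction: 0.200 + 0.5 × 0.05556 = 0.228, or 22.8 points.

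**4. Ratio.** 20.0/9.08 = 2.2. With Wald for both quantities the ratio is √[(1/72 + 1/24) × 96] = √5.333 = 2.3, whatever adherence is assumed.

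**5. Sensitivity of the difference (Wald).** 23.1 points at 50% adherence and 13.9 at 90%. If 95% are retained (10.5), 20.0/√0.95 = 20.5 at 75%.

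**6. Scope.** Steps 2 to 5 hold for the yes/no measure of 10.4.2. If the average rate in 10.8.3 is treated as a continuous score per woman, its precision depends on a standard deviation that the protocol does not give, so no figure can be derived.

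**The case against.** The strongest defence is that 10.4.2 is accurate on its own terms. It names its N, its quantity and its assumed value, and makes no claim about the difference. Adherence is secondary and has no hypothesis test, the sample size was taken from similar Phase 2a studies (10.4.1), and the planned intervals will show the true width whatever 10.4.2 says. All of that stands, and it limits the weight of the point. It does not explain why the only figure given is for an estimate that no section plans, while the stated objective has none.

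A second defence is that the average rate in 10.8.3 might be the proportion reporting uninterrupted use, averaged over the three visits, in which case a brief removal would count. That reading is possible. Scoring of questionnaire items is also commonly left to an analysis plan. But the protocol itself gives two descriptions that do not coincide, and the removal, expulsion and duration data collected under 7.8 would support either one.

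Three stronger readings are tempting, and the document does not support them:

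- A reader might infer that 9.1% is a calculation error. It reproduces; the mismatch is in what is estimated.
- A reader might expect the average rate to sit near its ceiling and hide removals. The protocol gives no distribution of time without the ring. Section 2.7.2 reports how often women in an earlier ring trial removed it for intercourse, but not for how long.
- A reader might put the 92% perfect adherence from that trial into the formula. There, perfect meant never out for more than an entire day, which is laxer than never out at all.

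**Conclusion.** The point holds as an internal mismatch. The 9.1% is a correct half-width for a pooled proportion that the analysis does not use. For the comparison that the objective and 10.8.3 call for, the yes/no measure at 75% in each arm gives about 20 points (19.4 to 22.8 by method), roughly 2.2 times the stated figure. The separate arms give 10.5 and 18.5 points. The size of the difference interval depends on the assumed adherence; that it is more than twice as wide as the pooled one, like for like, follows from the arm sizes alone.

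Independently of the numbers, the adherence measure in 10.4.2 is not the one described in 10.8.3, and the two need to be aligned. The consequence is confined to a secondary endpoint. Neither the sample size nor the primary safety analysis is affected.

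**What to change.** In 10.4.2, replace or supplement the 9.1% with the precision of the planned estimates: assuming 75% in each arm, 95% half-widths of about 10.5 points for dapivirine (n = 72), 18.5 for placebo (n = 24) and 20 for the 72 vs 24 difference.

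Use one adherence measure in 10.2, 10.4.2 and 10.8.3. The simplest choice is to add to 10.8.3 the between-arm difference in the proportion of women whose ring was never out over 12 weeks, with a Newcombe or exact interval, next to the average rate of use. Keeping the average rate as the main measure is also reasonable. In that case it should be defined, and 10.4.2 should state its precision with an assumed standard deviation, which the protocol does not currently give.

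The cost is a less favourable stated precision and one small extra analysis of a secondary endpoint. No further data collection or change in sample size is needed.

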7.7 Pharmacokinetics

The entire MTN-024/IPM 031 cohort will provide plasma for PK at Visits 3, 4 and 5.

A subset of approximately 30 participants across MTN-024/IPM 031 sites will be asked to provide vaginal fluid via tear test strip(s) at Visits 3, 4 and 5. These participants will be asked to opt-in to the PK subset.

An additional 15 participants will be asked to provide vaginal fluid via tear test strip(s) at Visits 3, 4 and 5 and will also provide two cervical tissue biopsy samples at a single time point, Visit 5. These participants will be asked to opt-in to the intensive PK subset.

A total of 96 participants will provide plasma, 45 participants will provide vaginal fluid via tear test strip(s) and 15 will provide cervical tissue.

Detailed instructions are provided in the MTN-024/IPM 031 SSP Manual available at <http://www.mtnstopshiv.org>.

Table 9: PK Specimen Collection Schedule

Visit	Specimens Collected for PK
Visit 3: 4-Week	
• Plasma (n= 96)• Vaginal fluid via tear test strip(s) (n= 45)
Visit 4: 8-Week	
• Plasma (n= 96)• Vaginal fluid via tear test strip(s) (n= 45)
Visit 5: 12-Week	
• Plasma (n= 96)• Vaginal fluid via tear test strip(s) (n= 45)• Cervical tissue (n=15)

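### Section 10.4.2 bases the vaginal-fluid detectable difference on 22 MTN-024 women, but 45 fluid donors at 3:1 imply about 34 on dapivirine, so the stated 1.04 SD / 135% is too large (a conservative error)

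*Protocol*

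**What the plan says.** The pharmacokinetic part of protocol section 10.4.2 opens its vaginal-fluid paragraph with "Approximately 45 women will provide vaginal fluid". It then gives a CV range, assumes 130%, and bases the calculation on a "comparison of MTN-013 (N=12) to MTN-024 (N=22), then with 5% type I error and 80% power". The result follows in the same sentence: "then with 5% type I error and 80% power, we can exclude a difference as large as 1.04 SD units or a 135% difference".

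Section 7.7 builds the 45 from two opt-in groups: about 30 women who give fluid only, and 15 more who give fluid and also cervical biopsies. Both groups give fluid at Visits 3, 4 and 5. The section sums up: "A total of 96 participants will provide plasma, 45 participants will provide vaginal fluid via tear test strip(s) and 15 will provide cervical tissue". Table 9 lists 45 fluid samples at each of the three visits.

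Allocation is 3:1 dapivirine to placebo (sections 6.1 and 10.6), with randomization stratified by site.

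The cervical-tissue paragraph of section 10.4.2 works from its full 15 women, "assuming N=11 due to 3:1 randomization".

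**The concern.** Only women on dapivirine can contribute to a comparison of dapivirine concentrations, so the MTN-024 group size should be the expected number of dapivirine women among the fluid donors. That is about three quarters of 45, not 22. The tissue paragraph applies this rule to all of its donors. The fluid paragraph does not arrive at the number the rule would give, and it offers no reason.

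The fluid comparison with premenopausal women is one of the stated aims of the PK work, and this is the only precision statement made for it. If the group size is wrong, the protocol misstates what that comparison can detect.

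**Working it through.** **Inputs**

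- 5% type I error, 80% power and MTN-013 N=12: section 10.4.2. Sidedness is not stated; two-sided is the version that reproduces the protocol's figure.
- CV: "If one assumes a CV% of 130"%, so the percent difference is d x 130%. Range given: "The CV% ranges from 118% to 153% depending on time, location, and formulation".
- Fluid donors: 45 = 30 + 15 (section 7.7, Table 9).
- Allocation 3:1 (sections 6.1, 10.6). Retention target 95% (section 10.5).

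**Method.** Two-sample t-test with equal variances. The standardised difference d is solved so that a noncentral t with df = n1 + n2 - 2 and noncentrality d / sqrt(1/n1 + 1/n2) gives 80% power at two-sided 5%.

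**Step 1: reproduce the protocol.** For 12 versus 22, df = 32, sqrt(1/12 + 1/22) = 0.3589, and the noncentrality needed is 2.889. So d = 2.889 x 0.3589 = 1.037, and 1.037 x 130% = 134.8%. This matches 1.04 SD / 135%. A normal approximation gives 1.005 SD (131%) and a one-sided t-test 0.91 SD (119%); neither matches. As a second check, 12 versus 11 gives 1.2265 SD, which agrees with the 1.23 SD stated for tissue. The method is therefore identified.

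**Step 2: expected dapivirine donors.**

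- All fluid donors: 45 x 3/4 = 33.75, about 34.
- With 95% retention: 33.75 x 0.95 = 32.1, about 32.
- Fluid-only group alone: 30 x 3/4 = 22.5, which is close to the 22 used.

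**Step 3: same method, consistent N.**

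| MTN-024 N (vs 12) | d (SD) | % at CV 130% | Power at 1.04 SD |
|---|---|---|---|
| 22 (as stated) | 1.037 | 134.8 | 80.2% |
| 32 | 0.971 | 126.2 | 85.1% |
| 33 | 0.966 | 125.6 | 85.4% |
| 34 | 0.962 | 125.0 | 85.8% |

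**Step 4: sensitivity.**

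- CV from 118% to 153%: N=34 gives 114% to 147%; N=22 gives 122% to 159%.
- Subset split: if the 45 were a random draw from the 96 randomized (72 on dapivirine), the dapivirine count would lie between 30 and 38 with 95% probability. That corresponds to 0.98 to 0.95 SD, or about 128% to 123%. A count of 22 or fewer would have probability of about 1 in 100 million, so chance imbalance does not explain 22.

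**The case against.** The strongest reply is that nothing turns on this. The calculation is correct for the inputs it names, and the error understates precision. The subset size was not derived from it: section 10.4.2 justifies the subset by logistics and the low likelihood of an important difference. The CV range alone moves the detectable difference by more than 30 percentage points, against about 10 for the correction. With either N, only a difference larger than the mean can be excluded. All of this stands and makes the point a modest one. It does not make the stated figure agree with 45 donors.

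It is also fair that 34 should not be fixed too exactly. The subsets are opt-in and randomization is not stratified by subset. PK sampling stops after product discontinuation (sections 7.5.3 and 7.5.4), and participants who leave are not replaced (section 10.5). A range of about 32 to 34 is the right way to state it.

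Two stronger readings are tempting, and the protocol supports neither. A reader might infer that fluid data from about 12 dapivirine women would be left out of the analysis. But N=22 appears only in a conditional planning sentence, and section 10.8.3 bases the PK analysis on the samples obtained, with no cap and no exclusion of the biopsy group. A reader might also take it as established that 22 was computed from the 30-woman fluid-only group. The arithmetic fits, but the protocol does not say so; it remains an inference.

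**Conclusion.** The point holds as an inconsistent input to a secondary-endpoint precision statement. With about 32 to 34 dapivirine women against 12, the detectable difference is about 0.97 to 0.96 SD, or 126% to 125% at a CV of 130%, rather than 1.04 SD / 135%. Power at 1.04 SD is about 85% to 86% rather than 80%.

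This assumes that the opt-in fluid donors split about 3:1, that losses are near the 5% implied by the retention target, and that the protocol's two-sided t-test and its percent scale are kept. The conclusion does not depend on how 22 arose. The gain is limited because the MTN-013 group is fixed at 12. The study is not underpowered because of this; it is slightly better placed than it says.

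**What to change.** In the vaginal-fluid paragraph of section 10.4.2, replace N=22 with about 34 (45 x 3/4), or about 32 if attrition is allowed for. Restate the detectable difference as about 0.96 to 0.97 SD, or 125% to 126%, at a CV of 130%. If only 22 women are meant to be counted, keep the figure and state the reason. The cost is a one-sentence edit, with no change to recruitment, sampling or the planned analysis.

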10.5 Participant Accrual, Follow-up and Retention

Based on previous studies of vaginal products, the accrual of 96 eligible participants will take approximately 12 months. Participants lost to follow-up and/or on temporary hold or permanent product discontinuation will not be replaced. However, every effort will be made to complete their regularly scheduled safety evaluations. Additionally, participants who are found to be HIV-infected and/or pregnant after enrollment will be terminated from the study and will not be replaced. Each site will target retention of 95% of enrolled participants over the 13-Week follow-up period.

10.6 Randomization

The participants will be randomized using permuted block randomization in a 3:1 ratio to the two arms of the study. Study arm randomization will be stratified by site to ensure balanced assignment for products at each site. The randomization scheme will be generated and maintained by the MTN SDMC.

10.7 Blinding

Study staff and participants will be blinded to the random treatment assignment of all study participants. All study product will be packaged in identical individual wrappers. Blinding will be maintained until all data are entered into the study database, all study endpoint data and other data included in the final analysis have been cleaned and verified, and the data are ready for final analysis. This will be explained to participants as part of the study.

There are no circumstances under which it is expected that unblinding will be necessary for the provision of medical treatment or to otherwise protect the safety of study participants. As described in Section 7.5.4, in the event that an investigator is concerned that a participant might be put at an increased risk by continuing product use, the Investigator may discontinue study product use by this participant; however, knowledge of the specific product to which the participant was assigned should not be necessary to guide further follow-up and/or treatment. If an Investigator feels that specific product knowledge is necessary to protect participant safety, the Investigator will notify the PSRT to review and approve the request.

